### HA: RRA > RRB

where RRA is the CR / VGPR rate in arm A (Carfilzomib / Ibrutinib) and RRB is the CR / VGPR rate in arm B (Ibrutinib). If the obtained one-sided p-value is less than or equal to 0.1 and the point estimate for the CR / VGPR rate of arm A is larger than that of arm B, it will be concluded that the Carfilzomib / Ibrutinib combination statistically significantly increases CR / VGPR rate compared to single agent Ibrutinib. Additionally, the two-sided 95% confidence interval (CI) of the rate difference (RRA-RRB) will be calculated as effect estimator. Further exploratory analyses of the primary study endpoint encompass the Cochran-Mantel-Haenszel (CMH) test of rate difference adjusting for stratification factors (MYD88 and CXCR4 status and number of prior lines). A CMH 95% stratified confidence interval (CI) of the rate difference (RRA-RRB) with each rate weighted by the number of patients in each stratification factor combination will be calculated as an effect estimator. Additionally, logistic regression models will be used to investigate the influence of putative risk factors on the CR / VGPR rate.

All secondary endpoints will be analyzed exploratory. Group comparisons in binary endpoints will be performed two-sided using the chi square test or Fisher's exact test as appropriate. Additionally, 95% CIs will be calculated for group differences. Survival times will be analyzed using the Kaplan-Meier estimator incl. 95% CI. Furthermore, the Cox Proportional Hazard model will be used to investigate the influence of putative risk factors on survival time. Group comparison in quality of life (ordinal endpoint) will be performed using the Wilcoxon rank-sum test. Additionally, the 95% CI will be calculated for the difference of the medians.

For safety analysis of the RCT, all adverse events will be listed and the frequencies of the most frequent will be calculated. Group comparisons (A vs. B) of frequencies of AEs and SAEs will be performed using the chi square test or Fishers exact test as appropriate.

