	where RRA is the CR/VGPR rate in arm A (Carfilzomib / Ibrutinib) and RRB is the CR / VGPR rate in arm B (Ibrutinib). If the obtained one-sided p-value is less than or equal to 0.10 and the point estimate for the CR / VGPR rate of arm A is larger than that of arm B, it will be concluded that the Carfilzomib / Ibrutinib combination statistically significantly increases CR / VGPR rate compared to single agent Ibrutinib. Additionally, the two-sided 95% confidence interval (CI) of the rate difference (RRA-RRB) will be calculated as effect estimator. Further exploratory analyses of the primary study endpoint encompass the Cochran- Mantel-Haenszel (CMH) test of rate difference adjusting for stratification factors (MYD88 and CXCR4 status and number of prior lines). A CMH 95% stratified CI of the rate difference (RRA-RRB) with each rate weighted by the number of patients in each stratification factor combination will be calculated as an effect estimator. Additionally, logistic regression models will be used to investigate the influence of putative risk factors on the CR / VGPR rate. All secondary endpoints will be analyzed exploratory. Group comparisons in binary endpoints will be performed two-sided using the chi square test or

	Fisher's exact test as appropriate. Additionally, 95% CIs will be calculated for group differences. Survival times will be analyzed using the Kaplan-Meier estimator incl. 95% CI. Furthermore, the Cox Proportional Hazard model will be used to investigate the influence of putative risk factors on survival time. Group comparison in quality of life (ordinal endpoint) will be performed using the Wilcoxon rank-sum test. Additionally, the 95% CI will be calculated for the difference of the medians. For safety analysis of the RCT, all adverse events will be listed and the frequencies of the most frequent will be calculated. Group comparisons (A vs. B) of frequencies of AEs and SAEs will be performed using the chi square test or Fishers exact test as appropriate.
Duration of recruitment	Q2 2024
Duration of the study for individual patient	Until disease progression or toxicity not tolerated by the patient plus follow-up or survival follow-up (max. 7 years after FPI)
Duration of the entire study	maximum 7 years after FPI (First Patient In 18.02.2021)

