In another large prospective randomized phase III study 150 patients with treatment naïve or relapsed WM in need of treatment were randomized between Ibrutinib / Rituximab (IR) Rituximab / Placebo (R). Median age was 69 years. High IPSSWM was reported in 38% of patients; 45% of patients were treatment naïve. With prolonged follow-up and a median duration of treatment of 29.5 months with IR and 15.5 months with R. Investigator-assessed major response rates ( $\geq$  PR) were 77% with IR vs 33% with R (P<0.0001); ORRs ( $\geq$  MR) were 95% vs 48% (P<0.0001), respectively. With continued IR treatment, 27% of patients achieved a VGPR compared to only 3% in the R arm. Major responses with IR stayed robust independent of MYD88/CXCR genotype. Overall time to major response was 2.0 months with IR vs 5.6 months with R (MYD88L265P/CXCR4WT: 1.8 vs 5.2; MYD88L265P/CXCR4WHIM: 2.9 vs 10.8; MYD88WT/CXCR4WT: 5.7 vs 5.7). Median investigator-assessed PFS was not reached with IR vs 20.3 months (95% CI: 11.6–31.3) with R (HR=0.219 [0.122–0.393]; P<0.0001); estimated 30mo PFS was 79% vs 41%. Among patients receiving IR, 30-months PFS estimates did not show any major differences among the different genotypes. The 30-months OS estimate was 93% with IR vs 90% with R; 31 patients on R crossed over to IR after IRC-confirmed PD. The AE profile in the IR arm was consistent with previous reports. Overall, grade  $\geq$  3 AEs occurred in 61% of patients in both arms. Incidence of grade  $\geq$  3 AEs was 53% during the first 12 months of treatment in the IR arm and increased 8% with longer follow up. SAEs occurred in 43% of IR patients vs. 33% of R patients. Similarly, incidence of SAEs was 39% during the first 12 months of treatment with IR and increased 4% with longer follow up.

These data and the approval of Ibrutinib have changed the therapeutic landscape in WM in shortest time and have fostered spread of chemotherapy-free approaches in the management of WM.

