#### Cause specific survival (CSS)

Cause specific survival is defined as the period from the randomization to death from lymphoma or lymphoma related cause (e.g. infections, bleeding, amyloid caused organ failure); death unrelated to WM is considered as a competing event.

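### Cause-specific survival makes non-WM death a competing event, but the only estimator the protocol assigns to survival times, Kaplan-Meier, can only censor it

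*Protocol*

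**What the plan says.** Protocol section 14.1.2 sets the endpoint: "Cause specific survival is defined as the period from the randomization to death from lymphoma or lymphoma related cause". It adds that "death unrelated to WM is considered as a competing event". The definitions of time to treatment failure, response duration, PFS and OS each carry a censoring rule. CSS has none and carries this competing-event statement instead.

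Protocol section 14.3 gives the methods for all survival-type endpoints together: "Survival times will be analyzed using the Kaplan-Meier estimator incl. 95% CI". For regression, "the Cox Proportional Hazard model will be used to investigate the influence of putative risk factors on survival time". The protocol names no cumulative incidence estimator and no other competing-risk method. The same section gives the status of these endpoints: "All secondary endpoints will be analyzed exploratory".

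**The concern.** A competing event is one after which the event of interest can no longer happen. Kaplan-Meier has no place for such an event. A patient who dies of something else is either counted as an event, which turns CSS into overall survival, or censored, which treats the patient as still able to die of lymphoma later. Under the CSS definition only censoring is possible.

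Read literally, section 14.3 therefore sets aside what section 14.1.2 declares. What is at stake is the absolute figure in the report, the probability of dying of lymphoma by a given year, which would come out too high. Non-WM deaths are foreseeable. Section 7.6.1 describes patients mostly of advanced age, and the synopsis lets the study run to a "maximum 7 years after FPI (First Patient In 18.02.2021").

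**Working it through.** **The plan's own figure.** The protocol gives no figure for CSS, so there is none to reproduce. Its sample size (16% vs 35%, one-sided 0.10, 80% power) reproduces at 47 per arm with 80.3% power, but it concerns the primary endpoint only and does not enter here.

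**Formulas**, assuming constant cause-specific hazards `h1` (lymphoma death) and `h2` (other death), with `h = h1 + h2`:

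- Kaplan-Meier with other deaths censored: `1-KM = 1 - exp(-h1*T)`
- True cumulative incidence of lymphoma death: `CIF = (h1/h) * (1 - exp(-h*T))`

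The first exceeds the second whenever `h2 > 0`.

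**Inputs from the protocol.**

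- Low-mortality anchor, section 7.4, randomized ibrutinib/rituximab (IR) versus rituximab (R) trial: "The 30-months OS estimate was 93% with IR vs 90% with R". This gives `h = -ln(0.93)/2.5 = 0.029` and `h = -ln(0.90)/2.5 = 0.042` per year.
- High-mortality anchor, section 7.1: median survival of 5 to 8 years from diagnosis. This gives `h = ln(2)/5 = 0.139` and `h = ln(2)/8 = 0.087` per year.
- Follow-up: from about 3.7 years (last patient in Q2 2024, study end in February 2028) to 7 years (first patient).

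**Assumed**, because the protocol does not give it: the WM share of deaths, `h1/h`, taken as 30%, 50% and 70%.

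**Results at a 50% WM share** (gaps taken before rounding):

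| All-cause mortality | T (years) | 1-KM | CIF | Gap (points) |
|---|---|---|---|---|
| 30-month OS 93% | 5 | 7.0% | 6.8% | 0.2 |
| 30-month OS 93% | 7 | 9.7% | 9.2% | 0.5 |
| 30-month OS 90% | 5 | 10.0% | 9.5% | 0.5 |
| 30-month OS 90% | 7 | 13.7% | 12.8% | 0.9 |
| Median 8 years | 5 | 19.5% | 17.6% | 1.9 |
| Median 8 years | 7 | 26.2% | 22.7% | 3.4 |
| Median 5 years | 5 | 29.3% | 25.0% | 4.3 |
| Median 5 years | 7 | 38.4% | 31.1% | 7.4 |

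Worked line (OS 93%, T = 7): `h1 = 0.0145`, so `1-KM = 1 - exp(-0.1016) = 0.0966`, and `CIF = 0.5*(1 - exp(-0.2032)) = 0.0919`.

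**Range over WM shares of 30 to 70%.** On the low anchor, with T from 3.7 to 7 years, the gap is 0.1 to 0.9 points (2% to 11% relative). On the high anchor, with T of 5 and 7 years, it is 1.5 to 7.4 points (6% to 36% relative).

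**Set against sampling error**, with about 49 patients per arm and censoring ignored: at 9% incidence the standard error is `sqrt(0.09*0.91/49) = 4.1` points; at 31% it is `sqrt(0.31*0.69/49) = 6.6` points.

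**The case against.** The strongest reply is that section 14.3 is a summary sentence. It neither names CSS nor says that non-WM deaths are censored, the definition in 14.1.2 shows that the issue was recognised, and the estimator could be settled in the SAP. The endpoint is exploratory, and at the mortality of the cited randomized trial the error is far below sampling error. The points on status and size stand. The appeal to the SAP does not fully answer the point, because the protocol does not leave the estimator open: it fixes one for survival times, makes no exception, and names nothing that handles a competing event.

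Three stronger readings are tempting, and the documents do not support them.

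- *That the comparison of arms on CSS is invalid.* Section 14.3 names no between-arm test for survival times, and a Cox model with competing deaths censored is a legitimate model of the cause-specific hazard. Suppose lymphoma hazards are 2% per year in both arms and other-cause hazards are 2% and 6%. At 5 years 1-KM is 9.52% in both arms, while the cumulative incidence is 9.06% and 8.24%. The identical Kaplan-Meier curves correctly show equal lymphoma hazards. The lower incidence arises only because more patients die of something else first.
- *That Gray's test is therefore required.* It addresses cumulative incidence, which is a different question from the cause-specific hazard. Choosing it is a preference, not the correction of an error.
- *That toxic deaths will be booked as lymphoma deaths by unblinded investigators.* The definition does mention a "lymphoma related cause (e.g. infections, bleeding, amyloid caused organ failure"), but these are examples and do not say that every such death counts. Section 14.1.2 does not say who assigns the cause. A separate treatment-related category would need a classification that the survival follow-up in Table 3 and the SAE rules in section 13.7 do not clearly collect.

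**Conclusion.** The concern holds as a contradiction between a definition and a method inside the protocol. Followed as written, section 14.3 gives a figure for lymphoma mortality that is too high and a CSS curve that is too low. The direction is certain once any non-WM death occurs; the size is not.

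The size rests on constant hazards, on an assumed WM share of deaths, and on two anchors that bracket the trial imperfectly. The 30-month figures come from other regimens and are extrapolated to 7 years. The median of 5 to 8 years is general and runs from diagnosis, not randomization. Seven years is also the longest possible follow-up, so the largest gaps lie in the tail, where few patients remain at risk.

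Within those limits the error is under 1 point if mortality resembles the cited randomized trial. It becomes material, at 1.5 to 7.4 points, only if mortality resembles the general figure. The primary test, the sample size and the other survival endpoints are untouched.

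**What to change.** In section 14.3:

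- Exempt CSS from the Kaplan-Meier sentence. Estimate the cumulative incidence of lymphoma-related death and of non-WM death by arm with the Aalen-Johansen estimator and 95% CI.
- State that any Cox model for CSS is a cause-specific hazard model, and report it for both causes of death.
- Keep Kaplan-Meier for OS, PFS, time to treatment failure and response duration, where death from any cause is an event.

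The cost is a change of wording and a standard analysis procedure. The only data needed are whether each death was WM-related, which the CSS definition already requires. No patients, visits or primary-analysis steps change.

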# 7. BACKGROUND INFORMATION AND STUDY RATIONALE

# 7.1 Waldenström's macroglobulinemia

Waldenström's macroglobulinemia (WM) is defined by a bone marrow infiltration by lymphoplasmacytic cells and the presence of a monoclonal immunoglobulin (Ig) M gammopathy in the peripheral blood. The clinical understanding of the disease has been greatly improved by the identification of internationally recognized criteria for initiating therapy, the description of an international prognostic index for patients requiring a first-line therapy and the definition of response criteria. These criteria are mainly based on the evolution of serum IgM concentration. However, delayed IgM monoclonal protein responses may cause important difficulties in response assessment. In addition, discrepancies between the kinetics of serum M protein reduction and the clearance of monoclonal B-cells from the bone marrow have been reported.

Despite continuing advances in the therapy of WM, the disease remains incurable with a median survival of 5 to 8 years from the time of diagnosis, thereby necessitating the development and evaluation of novel treatment approaches.

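### Cause-specific survival is defined with unrelated death as a competing event, but Kaplan-Meier is the only estimator named for survival times; it would overstate WM mortality, probably by a small amount

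*Protocol*

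**What the plan says.** Section 14.1.2 of the protocol sets the endpoint: "Cause specific survival is defined as the period from the randomization to death from lymphoma or lymphoma related cause", and "death unrelated to WM is considered as a competing event". Time to treatment failure, response duration, PFS and OS, in the same section, each carry a censoring rule. CSS has none and names a competing event instead.

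Section 14.3 gives the analysis: "Survival times will be analyzed using the Kaplan-Meier estimator incl. 95% CI". The regression follows: "Furthermore, the Cox Proportional Hazard model will be used to investigate the influence of putative risk factors on survival time". The synopsis repeats both. Neither place makes an exception for CSS, and no cumulative incidence or other competing-risk method appears anywhere in the protocol. Section 14.3 also fixes the status of the endpoint: "All secondary endpoints will be analyzed exploratory".

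**The concern.** Kaplan-Meier recognises only events and censored times. If unrelated deaths are counted as events, the curve is OS; to give anything specific to WM, they have to be censored. A censored patient is treated as still able to die of WM later, which a dead patient is not. One minus the curve is then the WM risk in a hypothetical setting without other deaths, under independence of the two causes. It is not the probability of WM death when unrelated death competes, and the 95% CI belongs to the hypothetical quantity.

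This is not a detail left open for a later analysis plan. The protocol names a method, and that method does not fit its own endpoint definition. At stake is the absolute WM mortality read from the CSS curve in a population that section 7.6.1 describes as mostly of advanced age, where some non-WM deaths must be expected.

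**Working it through.** The protocol states no figure for CSS, so there is nothing to reproduce.

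**Inputs**
- All-cause survival, favourable case: "The 30-months OS estimate was 93% with IR vs 90% with R" (section 7.4, phase III trial of ibrutinib plus rituximab). The 93% is used, with a constant hazard.
- All-cause survival, general background: "the disease remains incurable with a median survival of 5 to 8 years from the time of diagnosis" (section 7.1).
- Single-agent ibrutinib: 5-year PFS of 54% in mostly relapsed or refractory patients (section 7.6.2).
- Share of deaths due to WM, f: not in the protocol. Assumed 50%, varied from 30% to 70%.

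**Formulas.** Let S(t) be all-cause survival, with WM death a constant share f of the total hazard.
- Kaplan-Meier with competing deaths censored: 1 − KM = 1 − S^f
- Cumulative incidence of WM death: CIF = f × (1 − S)

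**Direction.** The difference 1 − S^f − f(1 − S) is zero at S = 1. Its derivative in S is f(1 − S^(f−1)), which is negative for 0 < f < 1 and S < 1, so the difference grows as survival falls. The sign does not need constant hazards: Kaplan-Meier weights each WM hazard increment by survival from WM alone, which is never below all-cause survival.

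**Size at f = 50%**

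| All-cause survival assumed | Time | S | 1 − KM | CIF | Excess (points) |
|---|---|---|---|---|---|
| 93% at 30 months | 2.5 y | 0.930 | 3.56% | 3.50% | 0.06 |
| same hazard | 5 y | 0.93² = 0.865 | 7.00% | 6.75% | 0.25 |
| same hazard | 7 y | 0.93^2.8 = 0.816 | 9.7% | 9.2% | 0.5 |
| median 8 years | 5 y | 0.5^(5/8) = 0.648 | 19.5% | 17.6% | 1.9 |
| median 8 years | 7 y | 0.5^(7/8) = 0.545 | 26.2% | 22.7% | 3.4 |
| median 5 years | 5 y | 0.500 | 29.3% | 25.0% | 4.3 |
| median 5 years | 7 y | 0.5^(7/5) = 0.379 | 38.4% | 31.1% | 7.4 |

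Varying f from 30% to 70% at 7 years gives an excess of 0.4 to 0.5 points (93% case), 2.8 to 3.4 (median 8 years) and 5.8 to 7.4 (median 5 years).

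**Which rows are plausible.** OS cannot lie below PFS, so the ibrutinib cohort in section 7.6.2 had 5-year OS of at least 54%. The 5-year-median rows set it at 50%, which is worse than the protocol reports for the control drug in mostly pretreated patients. The 7-year rows are also barely observable. Seven years is a calendar limit from first patient in on 18.02.2021, so follow-up ends about 18.02.2028. A patient entered at the end of Q2 2024 has about 3.6 years, and only the earliest patients approach 7.

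**Why one cumulative incidence curve is not enough.** Take a WM hazard of 0.06 per year and raise the other-cause hazard from 0.03 to 0.09. The 5-year WM cumulative incidence falls from (0.06/0.09)(1 − e^−0.45) = 24.2% to (0.06/0.15)(1 − e^−0.75) = 21.1%. One minus Kaplan-Meier stays at 1 − e^−0.30 = 25.9%. The WM curve alone would look better in an arm with more deaths from other causes.

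**The case against.** The strongest objection is that the effect is negligible here. Under the 93% figure the 5-year excess is 0.25 points, while a 95% CI around 7% with 47 patients per arm is about ±1.96 × √(0.07 × 0.93/47) = ±7 points. The endpoint definition is also broad: it counts deaths from infection or bleeding as lymphoma-related, which shrinks the competing share. This stands as an argument about size. Its limits are that the 93% comes from a combination arm and is extrapolated at a constant hazard.

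A second objection is that section 14.3 speaks of survival times in general and never assigns Kaplan-Meier to CSS by name, so an analysis plan could add cumulative incidence without breaking a named rule. That is fair against calling the two sections irreconcilable. It does not remove the mismatch: CSS is a survival time, and the text makes no exception.

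A reader might infer that the planned Cox model is wrong as well. It is not: with competing deaths censored, it estimates a valid cause-specific hazard ratio. That ratio simply does not translate directly into absolute WM mortality.

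A reader might also infer that Kaplan-Meier would conceal excess non-WM deaths on carfilzomib, given the cardiac events described in section 7.5. The documents do not support this. OS counts every death, and SAEs, including fatal ones in the reporting period, are compared by arm. What OS lacks is the split by cause.

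**Conclusion.** The mismatch is real and minor. Followed as written, section 14.3 gives a CSS curve that overstates WM mortality for the endpoint section 14.1.2 defines. With an assumed 50% WM share, the excess is about 0.25 points at 5 years and 0.5 at 7 years if mortality follows the 93% 30-month OS. It is about 2 to 3.5 points if median survival is 8 years, a general WM figure timed from diagnosis rather than randomization.

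A reader might take a bias of 4 to 7 points as the expected one. That needs the 5-year median, which the protocol's own ibrutinib data contradict, and its upper end needs follow-up that few patients will have. Nor does the protocol show that competing mortality is sizeable, since it gives no cause-of-death split. The primary test, sample size and type I error do not depend on CSS.

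**What to change.** In section 14.3 and the synopsis:
- Keep Kaplan-Meier for OS, PFS, time to treatment failure and response duration.
- For CSS, report the Aalen-Johansen cumulative incidence of WM-related death and of other death, by arm, with 95% CI. Show the two together.
- State that the planned Cox model for CSS, with competing deaths censored, estimates cause-specific hazards.

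The cost is a sentence or two in each place. The endpoint definition already requires deaths to be classified by cause, so no new data are needed, and standard software covers the estimator.

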## Quality of Life

Quality of Life will be assessed by the FACT-Lym questionnaire as indicated in Table 1, Table 2 and Table 3.

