## 14.2 Sample size estimation

## RCT - arms A and B:

The sample size calculation is based on the comparison of the primary endpoint (CR / VGPR rate) between the arms A and B using the one-sided chi-square test. According to Treon et al. (NEJM 2015) the CR / VGPR rate in WM patients treated with Ibrutinib is about 16%. We see an increase from 16% to 35% CR / VGPR as a clinically relevant increase, which corresponds to a more than doubling of deep remissions. Deep remissions correlate with PFS and the disease-free interval, thus we assume that the risk-benefit ratio justifies the addition of Carfilzomib when we achieve this improvement. Assuming a CR / VGPR rate of 35% in patients treated with Carfilzomib and Ibrutinib, this scenario requires a number of 94 patients (i.e. 47 patients per group) to reach a power of 80% at a one-sided type one error of 0.10. It is expected that the rate of withdrawal in the study is smaller than 5%. In addition to the drop-out rate of 5%, patients who were randomized but withdrew consent before the start of therapy may be replaced until the end of the recruitment period. According to this, the study will enroll approximately 99 patients in the arms A and B in total.

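### The quality-of-life comparison names no adjustment for the screening FACT-Lym score and pairs a rank-sum test with an interval that does not correspond to it; both cost precision, not validity

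*Protocol*

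**What the plan says.** Section 14.3, repeated under Statistical Methods in the synopsis, fixes the test: "Group comparison in quality of life (ordinal endpoint) will be performed using the Wilcoxon rank-sum test". The next sentence fixes the interval: "Additionally, the 95% CI will be calculated for the difference of the medians". No covariate, stratum or model is named for this endpoint. In the same section the primary endpoint also receives a stratified Cochran-Mantel-Haenszel analysis and logistic regression, and the survival times receive a Cox model.

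On collection, section 14.1.2 says: "Quality of Life will be assessed by the FACT-Lym questionnaire as indicated in Table 1, Table 2 and Table 3". Tables 1 and 2 place the questionnaire at screening, at cycle 13, every six months from cycle 25 and at end of treatment, in both arms. Table 3 adds the progression visit and six-monthly follow-up.

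On status, section 14.3 says: "All secondary endpoints will be analyzed exploratory". No effect size, standard deviation, alpha or power is given for quality of life.

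**The concern.** Two separate things are at issue.

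**Baseline.** Quality-of-life scores differ between patients before treatment starts. A two-sample rank test takes one value per patient and has no place for the screening score as a covariate. If raw cycle 13 scores are compared, all of that prior variation stays in the noise. If changes are compared, the screening score is used, but with a fixed weight of one that is generally not optimal. Cycle 13 is the only fixed-cycle questionnaire between screening and cycle 25, so it is the only scheduled one during the 24 carfilzomib cycles. Precision at that visit decides what the trial can say about the burden of adding infusions to an oral drug.

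**Interval.** Inverting the rank-sum test gives an interval for the Hodges-Lehmann shift, the median of all pairwise differences between arms. A difference of two sample medians is another statistic. A report could show p < 0.05 beside an interval that includes zero, with nothing in the plan to say which to read. An exploratory endpoint is read mainly through its estimate and interval.

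**Working it through.** **The plan's own figure first.** The protocol gives no quality-of-life figure, so the check starts from its sample size. Inputs from section 14.2: rates 0.16 and 0.35, one-sided alpha 0.10, power 80%. With mean rate 0.255,

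n = [1.2816·√(2·0.255·0.745) + 0.8416·√(0.16·0.84 + 0.35·0.65)]² / 0.19² = (0.790 + 0.506)² / 0.0361 = 46.6, so 47 per arm and 94 in total. Then 94/0.95 = 98.9, so 99.

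The stated 47, 94 and 99 are reproduced. 47 per arm is used below as the most that quality of life could have if 94 patients supply data.

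**Step 1: worth of baseline adjustment.** The correlation r between screening and cycle 13 is not in the protocol; 0.4 to 0.7 is assumed. With unit variance at each visit, the variance per patient is 1 for a raw score, 2(1 − r) for a change, and 1 − r² after adjustment. The gain in equivalent patients is therefore 1/(1 − r²) − 1 against raw scores, and 2(1 − r)/(1 − r²) − 1 = 2/(1 + r) − 1 against changes.

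| r | SE relative to raw, √(1 − r²) | Gain against raw | Gain against change |
|---|---|---|---|
| 0.4 | 0.917 | 19% | 43% |
| 0.5 | 0.866 | 33% | 33% |
| 0.6 | 0.800 | 56% | 25% |
| 0.7 | 0.714 | 96% | 18% |

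These formulas compare mean-based analyses. Under normality the rank test has efficiency 3/π = 0.955 relative to them.

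**Step 2: power for illustration.** Assumed: a true shift of 0.5 SD, two-sided alpha 0.05, 47 per arm. Power = Φ(e·√(47/2) − 1.96), with e = 0.5·√(3/π) for rank-sum on raw scores, that value divided by √(2(1 − r)) for rank-sum on changes, and 0.5/√(1 − r²) for ANCOVA. Simulated power (2,000 trials per scenario) is in brackets.

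| r | Rank-sum, raw | Rank-sum, change | ANCOVA |
|---|---|---|---|
| 0.3 | 66% (65%) | 52% (52%) | 72% (71%) |
| 0.5 | 66% (64%) | 66% (65%) | 80% (77%) |
| 0.7 | 66% (65%) | 86% (85%) | 92% (91%) |

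With 35 per arm supplying data, the approximation gives 53% for raw scores, 41 / 53 / 75% for changes and 59 / 68 / 83% for ANCOVA. With no true effect, the raw-score rank-sum test rejected in 4.8 to 5.0% of simulated trials, so its type I error is nominal.

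**Step 3: interval against test.** In the same simulations a bootstrap interval for the difference of medians was set beside the Hodges-Lehmann interval.

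- Mean width: about 1.04 SD for the medians, 0.84 SD for Hodges-Lehmann.
- Disagreement with the rank-sum decision at a 0.5 SD shift: 20.0, 19.6 and 21.1% of trials for r = 0.3, 0.5 and 0.7. With no effect: 3.6, 3.0 and 4.2%. Hodges-Lehmann: 0% throughout.
- Direction: at r = 0.3 the test was significant in 64.9% of trials and the median interval excluded zero in 47.4%, a net gap of 17.5 points. With 20.0% total disagreement, (20.0 + 17.5)/2 = 18.75% were significant tests beside an interval including zero, and 1.25% the reverse.

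The mismatch does not depend on r, because this test and these intervals use only the cycle 13 scores.

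**The case against.** The strongest case on the other side has five parts.

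- A reader might infer that the plan throws the screening score away. The text does not support that. It does not say whether raw scores or changes are compared, or at which visit, and a rank-sum test on changes fits the wording and uses the baseline. Those definitions may properly sit in a statistical analysis plan that is not at hand, so their absence is no fault. This stands, and it is why both readings are worked above. ANCOVA is at least as efficient as either in large samples under normal theory.
- A reader might infer that the interval is wrong. It is not. A difference of medians is a real, readable quantity, and under a pure location shift it targets the same parameter as Hodges-Lehmann. The defect is mismatch and extra width. The roughly 20% disagreement arises under an assumed 0.5 SD effect and falls to 3 to 4% with none.
- A reader might infer bias from chance baseline imbalance. Randomisation keeps the unadjusted test valid. The loss is efficiency.
- A rank test is a defensible robust choice for a score that the protocol calls ordinal, and ANCOVA adds a linear-model assumption. This is fair, and a reason to keep the rank test as sensitivity.
- A repeated-measures model would add little before cycle 25, since cycle 13 is the only fixed visit in between, and patients who progress move to survival follow-up. This also stands, so the proposal is confined to cycle 13.

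What the objections leave untouched is that section 14.3 does fix a test and an interval, that these two do not belong together, and that a baseline score is available for a more precise analysis.

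**Conclusion.** The point holds as a modest improvement to a valid exploratory analysis. Adjustment for the screening score is worth 19 to 96% more patients against raw scores, or 43 to 18% against changes, as r runs from 0.4 to 0.7. The two scales run in opposite directions, so the larger figures cannot be claimed without knowing which score is meant. At r = 0.5 both give 33%.

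The mismatch between test and interval holds whatever the correlation. In simulation the planned interval was about 24% wider than the matching one (1.04/0.84 = 1.24).

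The size rests on assumptions that the protocol neither gives nor contradicts: the correlation, equal variances at both visits, near-normal scores, a 0.5 SD effect for the power figures, and a bootstrap construction of the median interval. Nothing here touches the primary test, its alpha or the 94 and 99 patients.

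**What to change.** In section 14.3 and the synopsis, replace the quality-of-life sentences with text to this effect: FACT-Lym at cycle 13 is analysed by ANCOVA with arm and screening score as terms, and the adjusted mean difference is reported with its 95% confidence interval. The rank-sum test is kept as a sensitivity analysis and reported with the Hodges-Lehmann estimate and its 95% interval, in place of the difference of medians.

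The randomisation strata can be optional terms. Section 12.5 gives three genotype groups by two prior-line groups, six strata in all, or 99/6 = 16.5 patients per stratum on average, and fewer where a genotype is rare.

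The cost is wording and analysis code. The screening questionnaire is already collected, and no visit, patient or data item is added. The one small downside, reliance on a linear model, is covered by the retained rank test. As the trial is open label, the change should be fixed before quality-of-life data are looked at by arm.
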